Attachment

A014 \_RA phone script re communicating with Research Participants by Email.docx

Name

Comments

A014: Script for RA to discuss email communication with existing participants

Attachment Type

Data Collection Instrument

Attachment

Demographics RC Draft.docx

Name

Comments

Attachment Type

Data Collection Instrument

Attachment

Payment language RC Draft.docx

Name

Comments

language added to the end of follow up questionnaires completed online

## Administrative Details Form

### Protocol Details

9031

Protocol Type

Expedited

Billing Account #

Study Status

### Submission Details

9000

Submission Review Level

Expedited

9030

Expedited Category.

Category 5: Data or specimens that have been or will be collected for nonresearch purposes

Category 7: Survey, interview, focus groups, human factor, group behavior or characteristics

9002

Criteria for Approval. Select to confirm.

Approved: The criteria for approval of the research are satisfied in accordance with IU HRPP Policies, and applicable federal regulations.

### Protocol Determinations

9003

Protocol Level of Risk.

Minimal risk

9020

Is renewal required for this research?

No

9004

Check all determinations that need to be made.

Informed Consent Waiver

HIPAA Waiver

Vulnerable Population

Certificate of Confidentiality

9005

Informed Consent Waivers

Waiver of informed consent granted in accordance with IU HRPP Policies  
Waiver of documentation of informed consent granted in accordance with IU HRPP Policies.

9006

HIPAA Waivers

Participation

9010

Brief description of PHI - Participation

FGID Module: Data points collected for participation in the retrospective review of FGID module data include date(s) of visit, physician name, patient vitals and demographics, contact information, patient/parent answers to GI questions, who is answering the questions (parent or patient or both), and physician notes about GI diagnoses, treatments, and recommendations. Survey (online and phone): In addition to the FGID data points above, we will use parent and patient answers to the phone survey along with parent-reported demographics. Baseline retrospective review: DOB, date/diagnosis (ICD codes), Eskenazi clinic(s) of care Health care utilization retrospective review: The presence of outpatient sick visits within the CHICA system clinic for any complaint; The presence of outpatient sick visits within the CHICA system clinic with an associated GI billing code; The presence of visits to statewide providers, including inpatient hospital stays, outpatient clinic visits, and emergency room visits.; The occurrence of any GI-related testing and procedures – specifically radiologic, laboratory testing, endoscopy, and surgical procedures related to GI diagnoses; The use of any medications prescribed to treat Rome IV diagnoses – specifically acid-suppressants, antispasmodics, antidepressants, stool softeners and laxatives, and pro-motility agents.

9009

Participation HIPAA Waiver

Alteration of authorization criteria satisfied in accordance with 45 CFR 164.512(i)(2)(ii). Alteration of authorization approved in accordance with 45 CFR 164.512(i).

Waiver of authorization criteria satisfied in accordance with 45 CFR 164.512(i)(2)(ii).

Waiver of authorization approved in accordance with 45 CFR 164.512(i).

9011

Identify population(s) involved in this research.

Children

9012

Involvement of Children: Select to confirm.

The involvement of children in the research is appropriate in accordance with IU HRPP Policies.

9013

Children Category.

The involvement of children in the research satisfies the conditions of Category 404 in accordance with IU HRPP Policies.

9014

Parental Consent/Waivers. Choose all that apply.

The plan for soliciting parental/guardian permission is appropriate in accordance with IU HRPP Policies.

Waiver of parental/guardian permission granted in accordance with IU HRPP Policies.

Waiver of documentation of parental/guardian permission granted in accordance with IU HRPP Policies.

9015

Child Assent. Choose all that apply.

The plan for soliciting and documenting assent from children is appropriate in accordance with IU HRPP Policies.

Waiver of assent from children who are otherwise capable of providing assent granted in accordance with IU HRPP Policies.

9025

Certificate of Confidentiality.

The research is subject to the NIH Policy for Issuing Certificates of Confidentiality and therefore has been issued a Certificate.

9028

Other Determinations.

Systematic Pediatric Assessment of Rome Criteria (SPARC)

Principal Investigator: [name] MD

IRB Protocol # 1811325201

NCT04773158

April 1, 2019

**Sample Size and Power Estimates.** We calculated our sample size using the binary primary outcome (whether there was resolution of symptoms of a FGID by Rome IV criteria in children and adolescents or whether parental reassurance was achieved for infants). We wish to detect a 15% difference between the control and intervention clinics in the rate of the primary outcome. Since each FGID has a different estimated background rate of improvement without intervention, we estimated an overall weighted average improvement rate. We also took into consideration of differences of prevalence of different FGID diagnosis. Therefore, based on the data presented in Table 3, we estimated an overall improvement rate of 30% for the control clinics. Though we do not anticipate much variability in this rate at our six study clinics, we will use six different rates in a wide range, 15%, 20%, 25%, 30%, 35% and 40%, at baseline in order to estimate intra-clinic correlation. This translates to an intra-class correlation coefficient 0.007. However, for a conservative estimation of sample size, we will use intra-class correlation 0.014, two times the intra-class correlation we estimated.

Table 3. Data Utilized for Sample Size Calculations				
FGID Diagnosis	Estimated Baseline Improvement in 3 months	Prevalence	Unique CHICA patients/yr in age group	Minimum Time Required
Infant regurgitation (0-12m)	25%	10%	3172	10 months
Infant dyschezia (0-9m)	25%	5%	2640	26 months
Infant colic (0-5m)	48% 	10%	1584	26 months
Cyclic vomiting syndrome (3m-18y)	70% 	5%	22544	4 months
Functional nausea/vomiting (8-18y)	50%	5%	9702	8 months
Functional dyspepsia (8-18y)	25%	10%	9702	4 months
Irritable bowel syndrome (8-18y)	37.5% 	15% 	9702	4 months
Abdominal migraine (8-18y)	20%	2% 	9702	16 months
Functional abdominal pain - NOS	20%	15%	9702	4 months
Functional constipation (0-18y)	20%	20%	23336	3 months

Using a chi-square test and setting alpha at 0.05, the probability of detecting a statistically significant difference in the proportion of children with symptoms of any FGID with improvement in the primary outcome at 3 months from baseline between the intervention and the control group is 90%, with an effective sample size of 163 per group. Hence, the total effective sample size (n\*) is 326.

The unit of randomization is the clinic, but the unit of analysis is the individual patient. Since patients are nested within practice, responses from the patients within practice are likely to be

correlated. This intra-cluster correlation must be taken into account in the calculation of sample size and in the analyses. We computed the number of patients per clinic,  $m$ , required for the study, using the following equation:

$$m = \frac{1 - \rho}{\frac{k}{n^*} - \rho}$$

where  $\rho$  = intra-practice correlation  
 $k$  = number of clinics  
 $mk$  = total sample size  
 $n^*$  = total effective sample size =  $mk/DE$   
and  $DE$  = design effect =  $1 + \rho(m-1)$

Using 6 clinics and assuming intra-class correlation of 0.014, we need to recruit 224 families with a child between 0 and 18 per clinic. We anticipate that drop-out is not a major problem and unlikely to be more than 10% for the primary outcome. We will account for this factor by oversampling patients by 10%. According to the data presented in Table 3 and with an assumption that for each category of FGID diagnosis 50% of the patients will be in the control clinics and other 50% will be in intervention clinics, there will be about 5,500 patients/year/group with a FGID diagnosis. If we assume that only 66% of the parents will respond to the phone call at 3-month post baseline, we will have 3,630 patients/year/group. Therefore, the number of patients from which we are able to recruit is not a factor at all. We can have more than 90% power even to detect a 5% absolute difference with all available patients in one year.

**Data Analysis.** Baseline clinical and demographic data will be compared between the intervention and the control groups. Categorical variables will be examined using chi-square tests and continuous measures with Student's t-tests. The statistical analysis of the data will be performed using the SAS.

**Primary Outcome Analysis:** The primary outcome is whether there was resolution of symptoms of a FGID by Rome IV criteria in children and adolescents or whether parental reassurance was achieved for infants. For this dichotomous outcome, we will use a non-linear mixed-effects model and will adjust for potential confounders (fixed effects) and clinic effects (random effects). To be specific, if  $Y_{ik}$  is a binary variable indicating whether the  $k^{\text{th}}$  patient in the  $i^{\text{th}}$  clinic was reported a resolution of FGID symptom, we have

$$\text{logit}(Y_{ik} = 1) = \alpha_i + \mathbf{X}_{ik}\beta, \text{ where } \alpha_i \sim N(0, \sigma^2).$$

The random component  $\alpha_i$  correlates outcomes of patients cared by the same clinic. Physicians would not be considered as a nesting factor since the same patients at different visits may not be seen by the same physician. The vector  $\mathbf{X}_{ik}$  represents fixed covariates and  $\beta$  represents the corresponding coefficients. The fixed covariates will include critical covariates such as treatment group, gender, and other patient and clinic level characteristics. We will also examine potential interaction terms among the covariates, particularly interactions between treatment arm and other covariates. If there is a significant treatment difference, we will report the 95% confidence interval of the treatment difference after adjusting for all confounding factors. The model will be fitted by the SAS procedure NL MIXED.

**Secondary Outcome Analyses:** The additional time points of 1, 6, and 12 months will be modeled identically to the primary outcome analysis. Furthermore, we will have a number of secondary outcomes which are count data aggregated within the 12 months after initial Rome IV

diagnosis. We will use Poisson regression to model these count data. To adjust for the possible differences between the intervention and control groups, we will use an approach similar to the analyses of primary outcomes and again clinic will be considered as a cluster factor to take into consideration the correlation in count data within each clinic. Family and provider satisfaction scores will be analyzed using Student's t-test, as well as a linear mixed-effects model as with other outcomes.

Missing Data Analysis: We anticipate a low rate of missing data for the primary outcome since our CHICA system showed only 1.3% error rate due to omission of a data field. However, we anticipate a possible dropout rate of 10% for which we have adjusted the sample size. It is very unlikely that the dropout mechanism will depend on the unobserved outcome. Even if MNAR is true for certain subjects; given the low percentage of missing values, we think the bias induced is negligible. Under circumstances where compromise of power due to missing values is of concern, we will use a multiple imputation procedure to make use of all relevant observed data under the assumption that the data are Missing At Random (MAR). The SAS procedure MI and MIANALYZE will be used to implement the procedure.

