or presents to any primary care clinics in the Eskenazi health system which support general pediatric care, the patient (and/or parent) will be asked to complete FGID screening questions prior their provider visit as part of standard care. Rules have been established within EPIC to determine how often patients receive the FGID questionnaire to avoid redundancy, inappropriate use, and/or burden to the patient. Screening results will be available to physicians immediately, and physicians in the intervention clinics will have access to specific guidance for the diagnosis and treatment/management of the FGID, as well as information to share with families. Physicians may chose to document their FGID assessments and plans in the patient's EMR via EPIC. We hypothesize that automation of screening, diagnosis, and management of FGIDs will result in improved resolution of FGIDs (primary outcome), as well as decreased utilization of medical services (secondary outcomes). We propose to test this hypothesis using the following specific aims: Aim 1: Develop computer-based decision support system, to screen children 0 to 18 years of age for functional gastrointestinal disorders (FGIDs) using the Rome IV criteria, and provide guidance regarding diagnosis and management of probable FGIDs. (Please note that Aim 1 does not involve the use of human subjects/PHI.) Aim 2: Demonstrate the feasibility and effectiveness of the FGID Module to improve clinical care measures (e.g., resolution of Rome IV criteria) and reduce utilization of healthcare services (e.g. repeat outpatient visits, ED visits).

q22123

List and describe all research interactions and/or interventions, including the frequency and duration of procedures, and length of participation for individual subjects.

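### The SAP's six clinic rates give an ICC of about 0.037, not 0.007; at 0.037 the planned size has about 47% power for 30% versus 45%

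*SAP*

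**What the plan says.** The section Sample Size and Power Estimates of the SAP sizes the trial on the binary primary outcome. For the control arm, "we estimated an overall improvement rate of 30% for the control clinics". The target is given as follows: "We wish to detect a 15% difference between the control and intervention clinics in the rate of the primary outcome".

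For clustering, the SAP does not expect much variation between clinics but takes "six different rates in a wide range, 15%, 20%, 25%, 30%, 35% and 40%, at baseline in order to estimate intra-clinic correlation". It continues: "This translates to an intra-class correlation coefficient 0.007". It gives no formula for this step. It then says that "for a conservative estimation of sample size, we will use intra-class correlation 0.014, two times the intra-class correlation we estimated".

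The same section states 90% power with an effective size of 163 per group (326 in total). From this, with six clinics and an ICC of 0.014, it derives 224 families per clinic.

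**The concern.** For a binary outcome the ICC is the share of the total variance p(1−p) that lies between clinics. The value 0.007 looks like the between-clinic variance itself, before division by p(1−p). That divisor is about 0.2, so leaving it out makes the ICC about five times too small. Doubling the result does not make up for that.

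The ICC is the only clustering input to the sample size, and with six clinics it also caps the effective size. If it is too low, the plan promises power that more patients cannot supply, and a null result could be misread as evidence that the module does not work.

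**Working it through.** **Inputs from the SAP:** rates 15, 20, 25, 30, 35 and 40%; control rate 30%; difference 15 points; chi-square test at alpha 0.05; k = 6 clinics; n* = 326; m = 224 per clinic; 10% oversampling; 3,630 responders per group per year.

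**Assumptions:** two-sided test (the SAP does not say); three clinics per arm; contrast 30% versus 45%, because the Protocol's lay summary hypothesises that "automation of screening, diagnosis, and management of FGIDs will result in improved resolution of FGIDs (primary outcome").

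**1. The SAP's figure for m.** m = (1 − ρ)/(k/n* − ρ) = (1 − 0.014)/(6/326 − 0.014) = 0.986/0.004405 = 223.8. So 224 reproduces, and it depends directly on the ICC.

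**2. The ICC from the six rates.**
- Mean 0.275; population variance 0.00729; sample variance 0.00875.
- p(1−p) = 0.275 × 0.725 = 0.1994.
- ICC = 0.00729/0.1994 = 0.0366, or 0.00875/0.1994 = 0.0439 with the sample variance.
- With p = 0.30, so p(1−p) = 0.21: 0.0347 and 0.0417.
- ANOVA estimator at 224 per clinic: 0.039. Logit scale: 0.058 to 0.069.

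None of these is 0.007. The population variance, rounded, is. The value 0.014 is 0.014/0.0366 = 38% of the ICC from the listed rates. It corresponds to a clinic-rate SD of √(0.014 × 0.21) = 5.4 points, while the listed rates have an SD of √0.00729 = 8.5 points.

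**3. Design effect and effective size at m = 224.**
- ICC 0.014: DE = 1 + 0.014 × 223 = 4.12; effective size 672/4.12 = 163 per group.
- ICC 0.0366: DE = 1 + 0.0366 × 223 = 9.16; effective size 672/9.16 = 73 per group.

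**4. Limit with six clinics.** As m grows, the total effective size tends to k/ρ = 6/0.0366 = 164, below the 326 required. The formula for m has a positive solution only when ρ is below 6/326 = 0.0184, so at 0.0366 it has none.

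**5. Power for 30% versus 45%** (pooled chi-square, two-sided 0.05):

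| ICC | Patients per clinic | Effective n per group | Power |
|---|---|---|---|
| 0.014 | 224 | 163 | 80% |
| 0.0347 | 224 | 77 | 48% |
| 0.0366 | 224 | 73 | 47% |
| 0.0366 | 246 (10% oversampling) | 74 | 47% |
| 0.0366 | 1,210 (3,630/3) | 80 | 50% |
| 0.0366 | unlimited | 82 | 51% |
| 0.0439 | 224 | 62 | 41% |

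At ICC 0.0366 and 224 per clinic, the difference detectable with 80% power from a 30% control rate is 22.6 points. A t test on 4 degrees of freedom, which allows for there being only six clinics, gives about 31% power for 15 points.

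**6. A separate discrepancy.** For 30% versus 45%, 163 per group gives 80.2% power; 90% needs 217. So the ICC alone accounts for the fall from about 80% to about 47%, not from 90%. The contrast nearest to the SAP's 163 at 90% is 30% versus 15%, opposite to the hypothesis. On that contrast, power at ICC 0.0366 is 59% at 224 per clinic and 64% with unlimited patients.

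**The case against.** The strongest reply is that the listed rates are deliberately wide and the SAP expects little variation, so 0.037 describes an extreme scenario and not the expected one. This stands in part. The true ICC may well be below 0.037, and nothing in the documents shows that 0.014 is unrealistic. Adjustment for patient and clinic covariates in the primary model could also reduce the residual clinic variance, by an unknown amount. But the SAP offers these rates as the basis for its ICC and claims a twofold margin over them. That margin does not exist.

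A second reply is that the cause is inferred. That is correct, because no formula is shown. An ANOVA estimate depends on cluster size and would come near 0.007 at about 27 patients per clinic, but the SAP states no such size, and at 224 the estimate is 0.039. That the rates do not give 0.007 at the planned size does not rest on the inference.

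A third reply is that power below 50% depends on the contrast and the clinic size. It does: it applies to 30% versus 45% at 224 or 246 per clinic. Across the other cases above that use the chi-square test, power at 0.0366 runs from 50% to 64%, so neither 80% nor 90% is reached for 15 points.

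**Conclusion.** The concern holds. The listed rates imply an ICC of about 0.037 (0.035 to 0.044 on the proportion scale), and the 0.014 used for sizing is less than half of that. At the implied value the planned 224 per clinic gives about 47% power for 30% versus 45% (48% to 41% over that range), and recruiting more patients in six clinics cannot restore it. These figures assume a two-sided 0.05 test, three clinics per arm, equal clinic sizes and the SAP's own design-effect formula. They describe the scenario the SAP chose and do not predict the trial's actual ICC.

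**What to change.** - Replace 0.007 by the variance of the rates divided by p(1−p): 0.037, or 0.044 with the sample variance. Show the formula.
- Recompute the design effect, effective size and power, and state either the power for 15 points or the detectable difference (22.6 points at 80% power with 224 per clinic at 0.037).
- If 0.014 is considered realistic, justify it directly, for example from clinic-level data, as a clinic-rate SD of about 5.4 points. Stop describing it as twice the value from the listed rates.
- When restating power, write out the two rates compared, because 163 per group gives 80% and not 90% for 30% versus 45%.

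The cost is a recalculation and revised SAP wording. No new data are needed for the correction itself. The stated power becomes less favourable.

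### The 90% power for the primary outcome is not delivered: the plan's inputs give about 80% by large-sample theory and, with six randomized clinics, about 57% on 4 degrees of freedom

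*SAP*

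**What the plan says.** The SAP (Sample Size and Power Estimates) sets the target: "We wish to detect a 15% difference between the control and intervention clinics in the rate of the primary outcome". For the background rate, "we estimated an overall improvement rate of 30% for the control clinics". The protocol (section B, lay summary) gives the direction: automated screening and management "will result in improved resolution of FGIDs (primary outcome". The comparison is therefore 30% against 45%.

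The power statement begins "Using a chi-square test and setting alpha at 0.05, the probability of detecting a statistically significant difference" and, for the 3-month comparison of the two groups, concludes that this "is 90%, with an effective sample size of 163 per group". It continues: "Hence, the total effective sample size (n\*) is 326". With an ICC of 0.014 and six clinics, that total is converted to 224 families per clinic, with 10% oversampling for dropout. The same section says that more than 90% power is available even for a 5-point difference if all available patients in a year are used, having put 3,630 responders per year in each group.

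The SAP recognises the cluster design: "The unit of randomization is the clinic, but the unit of analysis is the individual patient". Its Primary Outcome Analysis specifies a logistic mixed model with a random clinic effect, fitted in SAS. Neither section mentions degrees of freedom, a small-sample correction or a cluster-level test.

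**The concern.** Dividing by the design effect enlarges the variance as if the between-clinic component were known. Here it has to be estimated from six clinics, and treatment does not vary within a clinic. With two arms, the comparison has about 6 - 2 = 4 df, so a test that holds 5% needs a critical value near 2.78 rather than 1.96. A power figure built on large-sample quantiles is then too high, even if every input is right.

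Two things are at stake. A null result from a trial described as 90% powered may be read as evidence that the module does not work, when the chance of missing the target effect was far above 10%. And since the primary analysis names no reference distribution for the treatment effect, whoever fits the model can choose one that does not control the error rate.

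**Working it through.** **Inputs.** From the SAP: control rate 0.30, difference 0.15, alpha 0.05, 163 effective per group (n* = 326), ICC 0.014, k = 6 clinics, m = 224 per clinic. From the protocol: improvement, so the intervention rate is 0.45. Assumed, because the documents do not state them: a two-sided test and three clinics per arm (the SAP assumes only that patients divide 50:50).

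**1. The clustering step reproduces.** m = (1 - 0.014)/(6/326 - 0.014) = 223.8, so 224. In reverse, the design effect is 1 + 0.014 × 223 = 4.122, and 3 × 224/4.122 = 163.0 per arm.

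**2. The 90% does not reproduce.** Large-sample power at 163 per group for 30% v 45% is 80.2% with the pooled chi-square and 80.8% unpooled. A one-sided test gives 87.8%. Sizes per group (pooled, two-sided): 163 for 80% power, 217 for 90%. The only variant that reaches 90% at 163 is a fall from 30% to 15% (90.4%), which is opposite to the hypothesis. This loss of about 10 points has nothing to do with degrees of freedom.

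**3. The number of clinics.** Noncentrality = 0.15/√[(0.30 × 0.70 + 0.45 × 0.55)/163] = 0.15/√(0.4575/163) = 2.83. Power from the noncentral t:

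| df | critical value | power |
|---|---|---|
| 3 (one clinic-level covariate) | 3.18 | 49% |
| 4 (clinics minus arms) | 2.776 | 57.2% |
| 5 (clinics minus one) | 2.57 | 62% |

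A simulation of a clinic-level t-test with beta-binomial outcomes (100,000 trials) gave 57.1%. From about 80% to 57% is a further loss of about 23 points.

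**4. Adding patients.** The planned oversampling (246 per clinic) gives 58.1%. At ICC 0.014 the effective size per arm cannot exceed 3/0.014 = 214, which is below the 217 of step 2 and gives at most 68.4% on 4 df.

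**5. Dependence on the ICC** (30% v 45%, 224 per clinic, 4 df):

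| ICC | effective n per arm | power |
|---|---|---|
| 0.007 | 262 | 77% |
| 0.014 | 163 | 57% |
| 0.037 | 73 | 31% |
| 0.044 | 62 | 27% |

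The last two rows are what the SAP's six listed rates (15% to 40%) imply. Their mean is 0.275 and their variance 0.00729 (divisor 6) or 0.00875 (divisor 5). Divided by 0.275 × 0.725 = 0.1994, these give 0.037 and 0.044, not 0.007.

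**6. The 5-point claim.** 3,630 per group is 1,210 per clinic. At ICC 0.014 the design effect is 1 + 0.014 × 1,209 = 17.93, leaving 202.5 effective per group. For 30% v 35% the noncentrality is 0.05/√[(0.21 + 0.2275)/202.5] = 1.08. Power is about 13% on 4 df, and 19% even with normal quantiles. Ignoring clustering altogether, 3,630 per group gives more than 99%, so the claim is consistent with no design effect having been applied.

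**7. A normal reference.** If the clinic variance is estimated on 4 df but 1.96 is used, the type I error is 2 × P(t₄ > 1.96) = 0.122. The simulation gave 12.0%, against 4.9% with the t reference.

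**The case against.** The strongest objection is to attribution. A reader might infer that the whole drop from 90% to 57% comes from having only six clinics. The documents do not support that: large-sample quantiles on the SAP's inputs give 80-81%, so about 10 of the 33 points belong to the 163. This objection stands.

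Nor is 57% the one true power. Three clinics per arm is an assumption, although a natural one; an unequal split would lower the power. The exact 4 df belong to an unadjusted clinic-level comparison. The planned model adds unspecified clinic-level covariates, each of which would cost a degree of freedom, while a clinics-minus-one rule gives 5. The figure also rests on an ICC that the SAP's own rates contradict. These points stand too, which is why ranges are given.

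A reader might also infer that the planned analysis will inflate the type I error. The SAP does not say so: its Primary Outcome Analysis includes a random clinic effect and is silent on the reference distribution. The 12% is what would follow from a normal reference. What is shown is an omission.

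Finally, the ICC may be low. At 0.007 and 224 per clinic, 4-df power is 77%, still short of 90%. Unlimited enrolment at that ICC would reach 92%, so the statement that patients cannot restore the power is tied to 0.014, the value the SAP chose to plan on.

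**Conclusion.** The concern holds in two separable parts. On the SAP's own inputs the power is 80-81% by the method that the SAP describes, not 90%. Once the between-clinic variance is treated as estimated from six clinics, it is about 57% on 4 df, with 49% to 62% across the defensible df. At ICC 0.014 the number of clinics is the limit, and enrolment cannot lift the 4-df power above about 68%. The claim for a 5-point difference fails by a wide margin, at about 13%.

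These results assume a two-sided 5% test, a 3:3 clinic split, equal clinic sizes and a test that holds its level. The ICC matters as much as the degrees of freedom: over 0.007 to 0.044 the 4-df power runs from 77% down to 27%. The stated power must be corrected, and the reference for the primary test should be settled before the data are analysed.

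**What to change.** 1. **Sample Size and Power Estimates.** Make one recalculation that corrects the 163, the ICC and the reference distribution together; changing only the df would replace one unsupported figure with another. State the clinic split and the sidedness. Use a t reference based on the number of clinics, and show power over a range of ICC, as in the second table above.
2. **5-point claim.** Withdraw it, or restate it on the same basis. Drop the reassurance that the supply of patients is no constraint, or add that the number of clinics is.
3. **Primary Outcome Analysis.** Prespecify the small-sample reference for the treatment effect: between-clinic degrees of freedom in the mixed model, or a cluster-level test. Name any clinic-level covariates in advance, since each costs a degree of freedom. If a permutation test is considered, note that a 3:3 split of six clinics has only 20 allocations, so its smallest two-sided p-value is 2/20 = 0.10; it could not reach 0.05 and would serve only as a supporting analysis.

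The cost is SAP wording and a less favourable stated power. Enrolment and conduct do not change. The low power remains, and the report should say so when interpreting a null result.

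### The stated 90% power at 163 effective patients per group is about 80% on the SAP's own inputs, and the 5-point power claim ignores clustering

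*SAP*

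**What the plan says.** All of this is in the SAP under Sample Size and Power Estimates.

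- **Effect and control rate:** "We wish to detect a 15% difference between the control and intervention clinics in the rate of the primary outcome", and from Table 3 "we estimated an overall improvement rate of 30% for the control clinics".
- **Power:** for a chi-square test at alpha 0.05, the probability of a significant difference between "the intervention and the control group is 90%, with an effective sample size of 163 per group", a total effective size n* of 326. Sidedness is not stated.
- **ICC:** six assumed clinic rates from 15% to 40% are used, and "This translates to an intra-class correlation coefficient 0.007". This is doubled to 0.014 as a conservative planning value.
- **Recruitment target:** with six clinics and "assuming intra-class correlation of 0.014, we need to recruit 224 families" per clinic, plus 10% for dropout.
- **Clustering:** "This intra-cluster correlation must be taken into account in the calculation of sample size and in the analyses".
- **Available patients:** after allowing for 66% response to the 3-month call, "we will have 3,630 patients/year/group". The paragraph ends: "We can have more than 90% power even to detect a 5% absolute difference with all available patients in one year".

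The Protocol (B-Lay Summary Research Design) gives the direction of the hypothesis: resolution improves under the intervention. The intervention rate is therefore 45%, although neither document prints that figure.

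**The concern.** For 30% against 45%, 163 per group is the familiar answer for 80% power, not 90%. The 163 is an effective size, already net of clustering, so no choice of ICC can make that sentence right. It is also the only basis for the recruitment target. If the true figure is 80%, the chance of missing the 15-point target is about 20%, twice what the SAP states.

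The 5-point sentence raises a second problem. With six clinics and a positive ICC, the effective sample size has a ceiling that more patients cannot lift. Very high power for a small difference therefore looks implausible, and the section itself insists that the correlation be allowed for. A reader who accepts either sentence would take a null result as stronger evidence against an effect than it is.

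**Working it through.** **Inputs.** p1 = 0.30, difference d = 0.15 (so p2 = 0.45), alpha 0.05, chi-square test, equal groups, k = 6 clinics, ICC rho = 0.014 (0.007 before doubling), 3,630 responders per group per year; all from the SAP. Two-sided testing is assumed.

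**1. Effective sample size for 15 points.** Let pbar = (p1 + p2)/2, A = sqrt(2 pbar(1 - pbar)) and B = sqrt(p1(1 - p1) + p2(1 - p2)). Here pbar = 0.375, A = 0.6847 and B = 0.6764.

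n per group = [1.960 A + z(power) B]² / d²

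- 80%: (1.3419 + 0.8416 × 0.6764)² / 0.0225 = 162.3, rounded up to **163**, the SAP's figure.
- 90%: (1.3419 + 1.2816 × 0.6764)² / 0.0225 = 216.8, rounded up to **217** (n* = 434).

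Power at 163 = Phi[(0.15 × sqrt(163) - 1.3419) / 0.6764] = Phi(0.847) = **80.2%**. Exact enumeration of the chi-square test gives 80.1%.

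**2. Other readings of the 90%.**

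| Reading | Power at 163 | n per group for 90% |
|---|---|---|
| 30% vs 45%, two-sided, pooled variance | 80.2% | 217 |
| 30% vs 45%, two-sided, unpooled variance | 80.8% | 214 |
| 30% vs 45%, one-sided | 87.8% | 177 |
| 30% vs 15%, two-sided | 90.4% | 161 |

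Only the last row reaches 90%. It describes a fall in resolution under the intervention, against the Protocol's hypothesis. Read as 15% rising to 30%, it contradicts the stated 30% control rate.

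**3. Patients per clinic.** The SAP's formula is m = (1 - rho) / (k/n* - rho).

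- n* = 326: 0.986 / (6/326 - 0.014) = **223.8**. The printed 224 reproduces, so it inherits the 80%.
- n* = 434: 6/434 = 0.01382 is below 0.014. The denominator is negative and there is no solution.

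**4. Power with clustering, 15 points.** n* = 6m / (1 + rho(m - 1)), which tends to 6/rho as m grows. The full one-year pool is 2 × 3,630 / 6 = 1,210 per clinic.

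| Patients per clinic, ICC 0.014 | n* | Power |
|---|---|---|
| 224 | 326.1 | 80.2% |
| 1,210 | 405.0 | 87.9% |
| no limit | 6/0.014 = 428.6 | 89.7% (90.1% unpooled) |

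**5. Power for 5 points (30% vs 35%), full one-year pool.**

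| Assumption | Design effect | Effective n per group | Power |
|---|---|---|---|
| No clustering | 1 | 3,630 | 99.5% |
| ICC 0.007 | 1 + 0.007 × 1,209 = 9.46 | 383.6 | 31.5% |
| ICC 0.014 | 1 + 0.014 × 1,209 = 17.93 | 202.5 | 18.8% |
| ICC 0.014, no limit on patients | – | 214.3 | 19.6% |

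A power of 90% for 5 points needs 1,842 effective patients per group (n* = 3,684), against the ceiling of 428.6. With 1,210 per clinic the ICC would have to be about (7,260/3,684 - 1)/1,209 = 0.0008 or lower.

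**6. Few clinics.** The figures above use normal critical values. A t reference on 4 degrees of freedom (six clinics less two arms) at n* = 326 gives about 57%.

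**The case against.** **The planning ICC is deliberately doubled.** At the SAP's own estimate of 0.007, 224 per clinic gives n* = 1,344 / 2.561 = 524.8 and 94.6% power for 15 points; about 146 per clinic would already give 90%. On that value the recruitment target is adequate by large-sample reckoning. This is a fair qualification to any claim that 224 is too few. It does not rescue the 90% sentence, which concerns effective patients and does not depend on the ICC. It does not rescue the 5-point sentence either (31.5% at 0.007).

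The 0.007 is itself doubtful. It matches the raw variance of the six listed rates (0.0073), whereas that variance divided by p(1 - p) at their mean of 0.275 is 0.00729 / 0.1994 = 0.037. The rates are an intentionally wide assumption, so 0.037 is not offered as the true ICC.

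**The lack of a solution at n* = 434 is a narrow miss.** Under the unpooled formula n* = 427.4 falls just below the ceiling of 428.6. That is correct, but it would take tens of thousands of patients per clinic, so the practical conclusion stands.

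**Saying that actual power is lower goes too far without conditions.** It should be tied to ICC 0.014. At that ICC the 4-degree-of-freedom figure supports it; a smaller true ICC would raise power.

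**This is only a planning statement.** The estimand, test and model are indeed unaffected. But it is the sole justification for the primary-outcome sample size, and it is wrong on its printed inputs.

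**Conclusion.** The concern holds. On the SAP's inputs, 163 effective patients per group give about 80% power for 30% against 45%, not 90%; 90% needs 217. This rests on two-sided testing and an improvement under the intervention, and one-sided testing does not restore 90%. The 224 per clinic carries the same 80% at the planning ICC of 0.014, where six clinics cannot take power beyond about 90%. The 5-point claim is true only for independent patients: with clustering the full one-year pool gives about 19% at ICC 0.014 and 31% at 0.007. The clustered figures are large-sample values with no correction for six clinics, so at ICC 0.014 actual power is lower. This must be corrected.

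**What to change.** 1. Replace the 90% sentence with wording such as: *With two-sided alpha 0.05, 163 effective patients per group (n* 326; six clinics of 224 analysed, ICC 0.014) give about 80% power for 30% vs 45%. This is a large-sample figure conditional on the ICC, with no correction for having only six clinics; at this ICC actual power is lower.*
2. Delete the 5-point sentence, or replace it with: *At ICC 0.014, 3,630 patients per group in one year give about 19% power for 30% vs 35%.*
3. If power is also shown at other ICC values, which would help the reader, recompute the ICC from the six rates first.

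The cost is one sentence rewritten and one deleted or corrected. Data collection and analysis are unchanged. The stated power becomes less favourable, and the sponsor must decide whether about 80% at ICC 0.014 is acceptable. At that ICC, recruiting more patients in the same six clinics would not in practice recover 90%.
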